9.5.3 Uterine Bleeding

The following analyses will be conducted based on 28-day windows during the placebo-controlled Treatment Period: $-28 - -1$, $1 - 28$, $29 - 56$, $57 - 84$, $85 - 112$, $113 - 140$, $141 - 168$, $169 - 196$, $197 - 224$, $225 - 252$, $253 - 280$, $281 - 308$, $309 - 336$. For each window, only subjects who were on study drug for the entire window will be included in the analysis.

- Continuous summary (mean, standard deviation, median, minimum, maximum) of the bleeding intensity. This is calculated for any bleeding/spotting days only for subjects who experienced bleeding/spotting. Bleeding categories are represented numerically as follows: Spotting = 1, Light = 2, Medium = 3, Heavy = 4.
- Continuous summary (mean, standard deviation, median, minimum, maximum) of the number of bleeding or spotting days. This is calculated for any subjects who experienced bleeding and/or spotting.
- Continuous summary (mean, standard deviation, median, minimum, maximum) of the number of bleeding only (no spotting) days. This is calculated for any subject who experienced bleeding, excluding those who experienced spotting only with no bleeding days.
- Continuous summary (mean, standard deviation, median, minimum, maximum) of the number of spotting days. This is calculated for any subject who experienced only spotting or no bleeding (i.e., subjects with at least 1 day of spotting and no days of light, medium, or heavy bleeding) in the given 28-day interval.
- Average number of uterine bleeding days by intensity. For each time window, the number of days when subjects report uterine bleeding will be summarized for each bleeding category, i.e., missing, no bleeding, spotting, light, medium

or heavy bleeding, spotting to heavy bleeding combined, and light to heavy bleeding combined.

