3.4 Benefits and Risks

Clinical studies with elagolix have demonstrated a statistically significant reduction in endometriosis-associated pain in premenopausal women with moderate to severe endometriosis-associated pain, including clinically meaningful improvements in DYS, NMPP, and in some cases, dyspareunia. Elagolix has been administered to over 3,700 subjects to date, and has been generally well tolerated. The most common adverse events associated with its use have included hot flush, headache and nausea.⁶ A modest degree of BMD decrease has been associated with elagolix, also in a dose-dependent manner, as expected from its mechanism of action. Hormonal add-back therapy may help to mitigate this effect. Menstrual cycle changes are also observed in individuals administered elagolix, and include lengthening of the cycle, and in some subjects, oligoor amenorrhea and/or irregular bleeding or spotting. Pregnancies have been observed in subjects exposed to elagolix, which is consistent with the dose-dependent effect on suppression of ovulation. To date, the benefit/risk profile of elagolix appears to remain favorable for the management of endometriosis-associated pain, and will be further defined by data from this Phase 3 trial.

Considering the Coronavirus Disease-19 (COVID-19) pandemic, the benefit and risk to subjects participating in this study has been re-evaluated. The use of elagolix plus E2/NETA addback provides a viable option to treat the chronic pain of women with endometriosis. Based on the limited information to date, no additional risk to study participants is anticipated with the use of elagolix in combination with E2/NETA in subjects who may contract COVID-19.

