An electronic patient-recorded outcomes device (e-Diary) will be provided to all subjects during Screening, and subjects will record daily entries through Treatment Month 12. The e-Diary contains training information for the subject and/or site staff will provide training on the required entries in the e-Diary. Subjects will also be instructed to complete the diary at approximately the same time(s) every day throughout the Screening Period through Month 12 of the Treatment Period, including prior to study visits as applicable. The e-Diary will also remind subjects about consistent use of acceptable forms of non-hormonal contraception.

Site staff should review subject e-Diary data periodically beginning at Screening through Treatment Month 12, as well as at every study visit, to ensure subject comprehension and completion. Subjects who are screen failures will be instructed to return the e-Diary device to the site. All subjects will be instructed to return the e-Diary device to the site at the Treatment Month 12 study visit or at the Premature Discontinuation visit (if prior to Treatment Month 12).

Subjects will use the e-Diary to record assessments of DYS, NMPP, dyspareunia and uterine bleeding, as well as the use of protocol-allowed rescue analgesic medications for

endometriosis-associated pain. Scores from these daily assessments collected during Screening will be used to evaluate subject eligibility for the study prior to randomization on Day 1. These assessments will continue to be completed daily through Month 12 of the Treatment Period or until a subject prematurely discontinues from the Treatment Period (if they discontinue prior to Treatment Month 12).

Based on the subject's response to the question "Did you have your period in the last 24 hours?" in the daily e-Diary, the subject will be asked to assess either their dysmenorrhea or non-menstrual pelvic pain as follows:

Dysmenorrhea (DYS)

[figure not shown]
Subjects will be asked to assess their DYS and its impact on their daily activities. Subjects will be prompted to "Choose the item that best describes your pain during the last 24 hours when you had your period."

None	No discomfort.
Mild	Mild discomfort but I was easily able to do the things I usually do.
Moderate	Moderate discomfort or pain. I had some difficulty doing the things I usually do.
Severe	Severe pain. I had great difficulty doing the things I usually do.

Non-Menstrual Pelvic Pain (NMPP)

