5.4 Removal of Subjects from Therapy or Assessment

Each subject has the right to withdraw from the study at any time. In addition, the Investigator may discontinue a subject from the study at any time if the Investigator considers it necessary for any reason, including the occurrence of an adverse event or noncompliance with the protocol. Subjects who withdraw from the study will not be replaced unless it is mutually agreed upon, in writing, by the Investigator and AbbVie. Subjects will be withdrawn from study drug treatment and/or the study if any of the following occur:

- The subject decides to withdraw consent for any reason
- The investigator believes it is in the best interest of the subject
- Clinically significant deterioration of the subject's medical status as determined by the Investigator
- The subject becomes pregnant or subject has a positive serum pregnancy test
- The subject has ALT or AST elevation > 5 times the upper limit of normal, confirmed upon repeat testing
- The subject develops clinically significant gynecological findings or condition on either the TVU (confirmed by repeat TVU and/or SIS and/or office hysteroscopy) or endometrial biopsy that in the opinion of the Investigator or AbbVie TA MD would preclude the subject from continuing in the Treatment Period due to safety reasons
- The results of any post-baseline DXA prior to Month 48 document a Z-score (for subjects ≤ 40 years of age) or T-score (for subjects ≥ 40 years of age) of

- < -2.5, a BMD decrease from baseline of > 8% in the lumbar spine, total hip or femoral neck, or due to TA MD assessment when the BMD percent change from baseline cannot be provided by the central reader
- The subject will require ongoing use of prohibited medications to manage or treat her endometriosis or endometriosis-associated pain in the opinion of the Investigator or AbbVie TA MD
- The subject requires use of prohibited medications to manage or treat bone mineral density changes during the Treatment Period as described in Section 5.2.3.3. Subject continuation in the Follow-Up Period is at the discretion of the AbbVie TA MD.
- The subject requires surgical intervention for treatment of endometriosis or uterine bleeding (e.g., laparoscopy, hysterectomy, ovarian cystectomy)
- The Investigator and AbbVie TA MD deems it appropriate to protect the subject because the subject expresses suicidal ideation on the C-SSRS or via clinical interview at any time during the study.

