3.4 Safety Endpoint(s)

The safety endpoints will be based on the following evaluations:

- Adverse events Monitoring
- Clinical laboratory tests
- Dual energy X-ray absorptiometry (DXA) scan
- Vital signs
- Endometrial biopsy
- Pelvic ultrasound (transabdominal ultrasound [TAU]/transvaginal ultrasound [TVU])
- Columbia Suicide Severity Rating Scale (C-SSRS)
- Pregnancy
- Uterine bleeding measured by e-Diary

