Appendix B. Definition of Adverse Events of Special Interest (AESI)

Adverse Events of Special Interest (AESI) will be identified using the following search criteria:

Item of Safety Interest	Method of Surveillance
Hot flashes	Non-bone related hypoestrogenic effects CMQ
Bone mineral density loss	Osteoporosis/Osteopenia SMQ
Anemia	Cases are identified through the Non-Hemolytic and Non-Aplastic Anemias CMQ Haematopoietic erythropenia SMQ
Bone Fractures	Osteoporosis/Osteopenia SMQ
Rash and hypersensitivity reactions	Anaphylactic reaction SMQ Severe cutaneous adverse reactions SMQ Drug induced rash CMQ
Lipid abnormalities	Dyslipidemia SMQ
Uterine bleeding change	Female reproductive bleeds CMQ
Endometrial safety	Uterine and fallopian tube neoplasms, malignant and unspecified SMQ Reproductive Premalignant Disorders SMQ
Hypoestrogenic AEs (excluding hot flashes, BMD loss, and fractures)	Non-bone related hypoestrogenic effects CMQ
Spontaneous abortion	Termination of pregnancy and risk of abortion SMQ
Obstetrical complications (maternal and infant)	Pregnancy, labor, and delivery complications and risk factors (excluding abortions and stillbirths) SMQ
Psychiatric events	Depression and suicide/self-injury SMQ
Cardiovascular events	Cardiac arrhythmias SMQ, Cardiomyopathy SMQ, and Ischemic heart disease SMQ
Thromboembolic events	Embolic and thrombotic events SMQ
Elevated hepatic transaminases	Drug related hepatic disorders – comprehensive search SMQ Enhanced pharmacovigilance hepatic terms (elagolix product specific) PMQ

[figure not shown]

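### The e-Diary bleeding summaries in SAP 9.5.3 discard a woman's recorded on-drug days in the 28-day window in which she stops study drug

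*SAP*

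**What the plan says.** Uterine bleeding is a named safety endpoint in SAP 3.4 ("Uterine bleeding measured by e-Diary"). SAP 9.5.3 sets out five descriptive summaries: "The following analyses will be conducted based on 28-day windows during the placebo-controlled Treatment Period". There is one pre-dose window (Days -28 to -1) and twelve on-treatment windows covering Days 1 to 336. One sentence governs all five: "For each window, only subjects who were on study drug for the entire window will be included in the analysis". No part-window, last-window or sensitivity version is given.

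The first four summaries (intensity, bleeding or spotting days, bleeding-only days, spotting days) are further limited to women with the event concerned; for the second, "This is calculated for any subjects who experienced bleeding and/or spotting". The fifth, days by intensity category, includes a no-bleeding category, but only within complete windows.

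Other parts of the plan bear on this:

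- Protocol synopsis (Statistical Methods, Safety Assessments), Protocol 8.1.7.1 and SAP 4.0: the safety population is everyone who took at least one dose. The synopsis then names uterine bleeding variables among the data to be summarised.
- SAP 9.1: safety analyses rest on observed data.
- Protocol 5.3.1.1: the diary is kept daily through Month 12 "or until a subject prematurely discontinues from the Treatment Period".
- Protocol 3.4 describes menstrual changes on elagolix, including "in some subjects, oligoor amenorrhea and/or irregular bleeding or spotting".
- Protocol 5.4 lists among the withdrawal reasons: "The subject requires surgical intervention for treatment of endometriosis or uterine bleeding".

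**The concern.** The inclusion rule depends on something that happens after randomization and may be caused by the outcome. If a woman stops because she is bleeding, the window removed is the one that contains the bleeding. Her diary entries for those days exist and were made on drug, yet they enter none of the five summaries.

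At stake is the only measure in the plan of how many days women bleed and how heavily. If stopping for bleeding differs between arms, the descriptive comparison of that burden is distorted in favour of the arm with more such stops. A woman who stops in her first four weeks contributes nothing on treatment, although the plan says all dosed women are in the safety analyses.

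**Working it through.** The plan states no figure for bleeding or for stopping because of bleeding, so there is nothing to reproduce. Its power statement concerns the responder endpoints and plays no part here.

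**Step 1: how often the rule bites.** Windows end on Days 28, 56, ..., 336. A woman with last dose on day d completes her current window only if d is a multiple of 28.

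- Of the 336 possible last-dose days, 12 are multiples of 28. The other 324 (324/336 = 27/28 = 96.4%) drop her from the window in which she stops.
- On-drug diary days lost = remainder of d divided by 28: 1 to 27 days, mean (1 + 27)/2 = 14.0 when a window is dropped.
- If d < 28 she enters no on-treatment window. Her earlier complete windows, if any, are kept.

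**Step 2: size, weighted by observed days.** All inputs are assumptions, since the documents give none:

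- full-window women average 3.0 bleeding days per 28;
- a fraction s of women stop in the window for bleeding, have 14 observed days and bleed on 80% of them (11.2 days);
- an equal fraction s stop for other reasons, have 14 observed days and bleed at the ordinary rate (1.5 days).

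Mean per 28 observed days
= 28 × [(1 − 2s)×3.0 + s×11.2 + s×1.5] / [(1 − 2s)×28 + 2s×14]
= (3.0 + 6.7s) / (1 − s).

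| s | All on-drug days | Full-window rule | Rise |
|---|---|---|---|
| 0.5% | 3.0335/0.995 = 3.05 | 3.00 | 1.6% |
| 1% | 3.067/0.99 = 3.10 | 3.00 | 3.3% |
| 1.5% | 3.1005/0.985 = 3.15 | 3.00 | 4.9% |
| 2% | 3.134/0.98 = 3.20 | 3.00 | 6.6% |

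The last row means 4% of an arm stopping per window. Sustained over twelve windows, that would remove 1 − 0.96^12 = 39% of the arm, so it suits an occasional bad window better than a steady rate.

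**Step 3: a different starting level.** Suppose full-window women average 5 bleeding days per 28, and a fraction q stop for bleeding after 14 observed days with b bleeding days (b = 10 to 14). The mean is 28 × [(1 − q)×5 + q×b] / [(1 − q)×28 + q×14]. This gives 5.04–5.06 at q = 0.5%, 5.08–5.12 at 1%, 5.15–5.23 at 2% and 5.38–5.59 at 5%. The shift is small unless several percent of an arm stop in one window.

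**Step 4: what could reverse the direction.** Under the Step 2 rates, a woman stopping for bleeding bleeds at 0.8×28 = 22.4 days per 28, an excess of 19.4 over 3.0. A woman who stops for another reason and is not bleeding at all has a deficit of 3.0. With equal observed days, 19.4/3.0 = 6.5 such women cancel one stop for bleeding.

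**Step 5: the baseline window.** Nobody is on study drug on Days -28 to -1. Read literally, the rule leaves that window empty. Nor does the rule say how the temporary interruptions of Protocol 5.5.4.1 count.

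**The case against.** The strongest reply is that the harm is recorded elsewhere. Uterine bleeding change is an adverse event of special interest (SAP Appendix B, "Female reproductive bleeds CMQ"), summarised under SAP 9.2.6. Treatment-emergent events run to 30 days after the last dose for women who discontinue (SAP 9.2.1), on all dosed women. Events leading to discontinuation are tabulated and listed (SAP 9.2.5), which is aimed at the woman described here. Protocol 6.1.1.1 keeps worsening endometriosis pain out of adverse event capture unless serious, but makes no such exception for bleeding. In SAP 9.5.4 the monthly amenorrhea rows use the same full-window denominator, but the row labelled Final is anchored on the last dose and can include women with at least 56 days on drug.

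All of that stands. A reader might infer from SAP 9.5.3 that bleeding in women who stop vanishes from the safety report; the documents do not support this. What none of these outputs gives is bleeding days or intensity in the stopping window: adverse event tables count events, and amenorrhea is yes or no.

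It also stands that requiring full exposure makes raw day counts comparable between women, that the fifth summary covers non-bleeders within complete windows, and that the bleeders-only summaries state their restriction openly alongside the amenorrhea proportions. The planned tables are legitimate. The gap is that nothing sits beside them.

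**Conclusion.** The point holds as a limited one. The full-window rule discards recorded on-drug diary days from a named safety endpoint, through an exclusion that may be informative, and sits poorly with the all-dosed, observed-data rules for safety.

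Two stronger readings should be resisted. First, a reader might infer that bleeding is necessarily understated. That depends on why women stop: Protocol 5.4 also lists pregnancy, bone density loss, raised transaminases and withdrawn consent, and such women may not be bleeding. The listed withdrawal for surgery shows that bleeding-linked stops are foreseen, not that they are common or differ by arm. Second, giving each stopper the weight of a full-window woman yields 3.0 + 19.4s, that is 3.10 to 3.39 for s from 0.5% to 2% (3% to 13%). That lets 14 observed days count as 28; weighting by observed days roughly halves the rise, to about 2% to 7%.

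That range rests wholly on the Step 2 assumptions. SAP 9.5.3 specifies no test, so no error rate and no primary conclusion is affected. This is a cheap improvement to a descriptive safety analysis.

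**What to change.** In SAP 9.5.3, keep the planned tables and:

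1. Add a summary for all dosed women that counts every on-drug diary day up to the last dose, reported by window and arm as bleeding, spotting and heavy-bleeding days per 28 observed on-drug days, weighted by observed days and with non-bleeders as zero.
2. Report how many women each full-window summary excludes, by arm and reason for stopping.
3. Exempt the Day -28 to -1 window from the on-drug rule, and state how days of temporary interruption are counted.

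The cost is SAP wording and a little more programming on e-Diary data already collected. No visit, assessment or clinical rule changes. The downside is noisier individual values from short partial windows, which weighting by observed days limits in the arm-level figures.

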9.5.4 Amenorrhea

Determination of amenorrhea depends on a subject indicating both no menstrual period and no uterine bleeding as collected in the daily e-Diary. Missing responses for uterine bleeding question will be treated as "No Bleeding." Missing responses for the menstrual period question will be treatment as a response of "No" to the menstrual period question. The determination of amenorrhea also requires data indicating "No Bleeding" and the absence of a menstrual period for a minimum number of 56 days.

The number and percentage of subjects with amenorrhea by month based on a 56-day window ([Table 2](#)) will be summarized by treatment group. the numerator is the number of subjects on treatment who did not bleed during the specified time window and the denominator is the number of subjects on drug for the full window. To be considered amenorrheic, a subject must have answered "No Bleeding" at least once during each 28-day period of interest.

Table 2. Monthly Summary of Amenorrhea – 56 days

Basis	Time Interval	Amenorrheic Status
Amenorrheic at least 56 days prior to last dose date	Month 2 (Days 2 – 56)	Subjects did not bleed during Study Days 2 – 56 and subjects answered the e-Diary at least once during Days 2 – 28 and Days 29 – 56 (Truncated, 55 day window)
	Month 3 (Days 29 – 84)	Subjects did not bleed during Study Days 29 – 84 and subjects answered the e-Diary at least once during Days 29 – 56 and Days 57 – 84
	Month 4 (Days 57 – 112)	Subjects did not bleed during Study Days 57 – 112 and subjects answered the e-Diary at least once during Days 57 – 84 and Days 85 – 112
	Month 5 (Days 85 – 140)	Subjects did not bleed during Study Days 85 – 140 and subjects answered the e-Diary at least once during Days 85 – 112 and Days 113 – 140
	Month 6 (Days 113 – 168)	Subjects did not bleed during Study Days 113 – 168 and subjects answered the e-Diary at least once during Study Days 113 – 140 and Days 141 – 168
	Month 7 (Days 141 – 196)	Subjects did not bleed during Study Days 141 – 196 and subjects answered the e-Diary at least once during Days 141 – 168 and Days 169 – 196
	Month 8 (Days 169 – 224)	Subjects did not bleed during Study Days 169 – 224 and subjects answered the e-Diary at least once during Days 169 – 196 and Days 197 – 224
	Month 9 (Days 197 – 252)	Subjects did not bleed during Study Days 197 – 252 and subjects answered the e-Diary at least once during Days 197 – 224 and Days 225 – 252
	Month 10 (Days 225 – 280)	Subjects did not bleed during Study Days 225 – 280 and subjects answered the e-Diary at least once during Study Days 225 – 252 and Days 253 – 280
	Month 11 (Days 253 – 308)	Subjects did not bleed during Study Days 253 – 308 and subjects answered the e-Diary at least once during Study Days 253 – 280 and Days 281 – 308
	Month 12 (Days 281 – 336)	Subjects did not bleed during Study Days 281 – 336 and subjects answered the e-Diary at least once during Days 281 – 308 and Days 309 – 336
	Final (last 56 days including last dose day)	Subject did not bleed during the last 56 days on treatment and answered the e-Diary at least once during the periods [last dose date – 55, last dose date – 28] and [last dose date – 27, last dose date]

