- 8. Prior to Study Day 1, subject must have two documented menstrual cycles with a cycle length of 21 38 days. A minimum of one full menstrual cycle (i.e., including 2 menses or periods) must be documented in the e-Diary; however, the start of the previous menstrual cycle may be based on the subject's historical recall and must be appropriately recorded in the subject's source documents.
- 9. Subject has a minimum of 45 days of e-Diary entries during the Screening Period.
- 10. Subject must have the following documented in the e-Diary during the last 35 days prior to Study Day 1:
 - At least 2 days of "moderate" or "severe" DYS AND either,
 - At least 2 days of "moderate" or "severe" NMPP and an average NMPP score of at least 1.0,
 OR
 - At least 4 days of "moderate" or "severe" NMPP and an average NMPP score of at least 0.5.

Rationale for Inclusion Criteria

- This is standard criterion in accordance with harmonized Good Clinical Practice (GCP)
- 2 4, 8 10 These criteria were selected to ensure an appropriate subject population of premenopausal women with moderate to severe endometriosis-associated pain
- The impact of elagolix on pregnancies or breastfed infants is unknown and there is a possible risk of miscarriage due to changes in hormone levels; therefore, these criteria ensure pregnant women are not enrolled into the study and adequate precautions are taken to avoid pregnancy during study participation
- 7 To ensure general good health and the safety of subjects

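### The amenorrhea rule reads blank diary days as no bleeding and asks for one answer per 28-day half, so a woman who still menstruates can be counted as amenorrheic on as few as two entries

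*SAP*

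**What the plan says.** SAP Section 9.5.4 defines amenorrhea from two daily e-Diary questions, uterine bleeding and menstrual period, over 56-day windows (55 days for Month 2).

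- Blank bleeding answers: "Missing responses for uterine bleeding question will be treated as" no bleeding.
- Blank period answers: "Missing responses for the menstrual period question will be treatment as a response of" no.
- Duration: the determination also calls for data showing no bleeding and "absence of a menstrual period for a minimum number of 56 days".
- Minimum evidence in the text: an answer of no bleeding "at least once during each 28-day period of interest".
- Minimum evidence in Table 2 (Month 3 row): no bleed in the window, and "subjects answered the e-Diary at least once during Days 29 – 56 and Days 57 – 84". The other rows, including Final, follow the same pattern.
- Denominator: "the denominator is the number of subjects on drug for the full window", whatever the state of the diary.

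The diary is meant to be daily: under Protocol Section 5.3.1.1, "subjects will record daily entries through Treatment Month 12". The one diary-completeness minimum in the protocol is 45 days of entries during Screening (Protocol Section 5.2.1). None is set for the amenorrhea windows, and no sensitivity analysis is given. In SAP Section 9.5.3, the summary of bleeding days by intensity keeps missing days as a category apart from days without bleeding.

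**The concern.** A blank day carries no information about bleeding, yet here it counts as evidence of none. The requirement of 56 days without bleeding can then be met almost entirely by imputed days. The same blank day is missing in one table (9.5.3) and bleed-free in the next (9.5.4).

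The text and Table 2 also differ. The text wants an explicit answer of no bleeding; Table 2 wants only that the diary was answered. They part ways when a woman answers the diary but leaves the bleeding question blank, and a programmer needs one rule.

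What is at stake is how the monthly amenorrhea table is read. It is given by treatment group for Months 2 to 12 and for the last 56 days on treatment. Its percentages mix the effect of treatment on bleeding with the pattern of diary completion.

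**Working it through.** The plan states no amenorrhea rate or precision, so there is no figure to reproduce. The check applies the rule as written.

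**Inputs from the documents.** 56-day window in two 28-day halves; at least one answer of no bleeding per half; blanks imputed as no bleeding and no period; denominator unaffected by diary completion (SAP 9.5.4). Daily entries are due (Protocol 5.3.1.1). At entry the "subject must have two documented menstrual cycles with a cycle length of" 21 to 38 days (Protocol 5.2.1), so 1 to 3 periods fall in 56 days if cycles continue.

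**Assumptions (the documents give neither figure).** b bleeding days per 28-day cycle, base case 5, range 3 to 7; each diary day completed independently with probability c.

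**Step 1: least evidence accepted.** 2/56 = 3.6% of days answered, so up to 54/56 = 96.4% may be imputed.

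**Step 2: menstruating woman, blanks at random.** She is counted as amenorrheic if none of her 2b bleeding days is recorded and each half holds at least one of its 28 − b other days:

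F(c) = (1−c)^(2b) × [1 − (1−c)^(28−b)]²

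For b = 5, c = 0.2: 0.8^10 × (1 − 0.8^23)² = 0.1074 × 0.988 = 0.106.

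| Completion c | b = 3 | b = 5 | b = 7 |
|---|---|---|---|
| 5% | 38% | 29% | 21% |
| 10% | 46% | 29% | 18% |
| 20% | 26% | 11% | 4.3% |
| 30% | 12% | 2.8% | 0.7% |
| 40% | 4.7% | 0.6% | 0.1% |
| 50% | 1.6% | 0.1% | 0.01% |

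Simulated with 5 bleeding days and random cycle phase, the chance at 20% completion is 5.6% for a 21-day cycle and 21% for a 38-day cycle; at 50% it is 0.02% and 1.5%.

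**Step 3: menstruating woman, bleeding days skipped.** If she answers all 23 other days in each half and none of the 5 bleeding days, completion is 46/56 = 82% and she is classed as amenorrheic with certainty. If she completes 80% of other days and a share d of bleeding days, the chance is (1−d)^10 × (1 − 0.2^23)²: about 100% at d = 0, 35% at 10%, 11% at 20%, 2.8% at 30% and 0.1% at 50%.

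**Step 4: truly amenorrheic woman.** She is counted only if both halves hold an answer: T(c) = [1 − (1−c)^28]². This is 99.6% at 20% completion, 90% at 10% and 58% at 5%. Otherwise she stays in the denominator as not amenorrheic.

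**Step 5: difference between arms.** With true proportion a, the expected reported proportion is a·T + (1−a)·F. If both arms share the same c and b, the reported difference is (a₁ − a₀)(T − F). For b = 5 the multiplier is 0.996 − 0.106 = 0.89 at 20% completion, 0.90 − 0.29 = 0.61 at 10%, and 0.999 at 50%. The difference shrinks.

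**The case against.** One recorded bleeding or period day in the window takes a woman out of the numerator. With blanks at random the error is therefore small above about 30–40% completion in the base case. Sparse diaries are also discouraged: screening needs 45 days of entries, women unable or unwilling to complete the diary are excluded (Protocol 5.2.2), staff review entries at every visit through Month 12 (5.3.1.1), and non-compliance with the diary is a ground for withdrawal (5.4). The missing-day category in SAP 9.5.3 would show an arm difference in blanks. SAP 9.5.4 specifies no test, and amenorrhea is neither a co-primary (SAP 3.1) nor a ranked secondary endpoint (SAP 3.2). The 56-day wording can be read as a window length applied after imputation.

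All of this stands as a limit on size and importance. It does not change the rule: the compliance measures set no completeness minimum for these windows, and none of them deals with skipping on bleeding days.

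A reader might go further in three ways that the documents do not support:

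- *Menstruating women with sparse diaries are, as a rule, classed as amenorrheic.* They can be. For a woman with exactly one random entry in each half, the chance is (23/28)² = 67%, but that is an assumed extreme. With exactly 7 entries per half it is 4.3%, and with 10 it is 0.8%.
- *Amenorrhea rates rise whenever compliance falls.* Step 4 works the other way for truly amenorrheic women, and for menstruating women the chance stops rising at very low completion (29% at both 5% and 10% in the base case).
- *The rule manufactures a drug effect.* Step 5 points to a narrower difference when completion is equal. A wider one needs completion, bleeding days or skipping to differ between arms in a particular way, and the documents report none of these.

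**Conclusion.** The point holds as a defect of definition. The rule allows a woman who still menstruates to be counted as amenorrheic on two entries out of 56, and counts a woman with an empty half as not amenorrheic.

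With blanks at random, 5 bleeding days per 28 and a 28-day cycle, the first error is about 29% at 10% completion, 11% at 20%, 3% at 30% and 0.1% at 50%. With fewer bleeding days or longer cycles it is larger. If bleeding days are the ones skipped, it approaches certainty even at about 82% completion. These figures rest on assumed bleeding days, completion and missingness patterns.

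The direction of any bias between arms is not established; equal completion would probably narrow the difference from placebo. The co-primary and ranked secondary conclusions are untouched. The plan should be corrected, but the stakes are those of a descriptive safety table.

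**What to change.** In SAP Section 9.5.4:

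1. Make a woman evaluable for a window only if she has a pre-set minimum of completed diary days in each 28-day half, for example 20 or more. Otherwise set amenorrhea to missing and leave her out of that month's denominator.
2. Align the text with Table 2 on whether the required answer is an explicit no bleeding or any diary answer.
3. Show diary completion by arm and month beside the amenorrhea table.
4. Keep the present rule as a sensitivity table.
5. Add a table that counts missing days as bleeding, to bound selective skipping.

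Item 5 is needed because a 20-day minimum removes nearly all of the random-blank error (below one in ten million at 50% or 80% completion in the base case) but not selective skipping. A woman with 5 bleeding days per 28 has 23 other days and still passes; only a minimum of 24 would force a bleeding day into the record. The bound is deliberately harsh: a truly amenorrheic woman at 95% random completion has a full 56-day record with chance 0.95^56 = 6%.

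The cost is SAP wording and a few extra tables from data already collected, with a somewhat smaller evaluable denominator and some selection on compliance. Protocol Amendment 7 says all subjects are past Month 36, so diary collection has ended. If the Month 12 tables have already been produced, they can be re-run from the same data, with the chosen minimum labelled post hoc.
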